8.3.4 Progression-free Survival

PFS is defined as the time from randomization to the time of disease progression or relapse (according to RECIST 1.1) or death, or to the date of last tumor assessment without any such event (censored observation) and includes any of the following:

- Occurrence (clinically or imaging signs) of any new lesion
- Increase in measurable and/or non-measurable tumor as defined by the RECIST 1.1 criteria

8.4 Pharmacokinetics

Please refer to the laboratory manual for detail instructions on processing of the pharmacokinetic samples.

8.4.1 APR-246

A full PK profile will be taken during Cycle 1 from patients selected for ECG Holter testing (Table 8), followed by sparse PK sampling from Cycle 2 onwards (Table 9).

For all other patients, sparse PK sampling will be done from Cycle 1 until the last Cycle (Table 9).

The objective of the sparse PK sampling scheme is to enable construction of individual PK parameters (AUC and C_{max}) for correlation with efficacy and safety. The PK of APR-246 follow a bi-exponential decline and therefore a minimum of three samples are needed to construct the PK individual profiles.

The PK sampling scheme allows for some flexibility in the timing of the blood sampling and whenever possible time windows for sample collection are given. Nevertheless it is critical for the PK evaluation that the exact times of dose administration and PK sample collection are recorded on each occasion.

Table 8. PK Blood Sampling Time Points for APR-246 During Cycle 1 (Patients Selected for ECG Holter)

Day 1	Before infusion	0-2 hrs prior to APR-246 infusion
	During infusion	5-15 min prior to end of infusion
	After infusion	15 mins +/-3 min AFTER the end of infusion
		1 hr +/-5 min AFTER the end of infusion
		3 hrs +/-15 min AFTER the end of infusion
Day 2	Before infusion	0-30 min prior to APR-246 infusion
Day 4	Before infusion	0-30 min prior to APR-246 infusion
	During infusion	5-15 min prior to end of infusion
	After infusion	15 min +/-3 min AFTER the end of infusion
		1 hrs +/-5 min AFTER the end of infusion
		3 hrs +/-15 min AFTER the end of infusion
Day 5	No infusion	12-24 hrs AFTER the end of Day 4 infusion

Table 9. Sparse PK Blood Sampling Time Points for APR-246

D1 C1*-final cycle	Before infusion	0-2 hrs prior to APR-246 infusion
	At end of infusion	+/-5 min relative to the end of infusion
	After infusion	30-60 min AFTER infusion
D4 C1*-final cycle	Before infusion	0-2 hrs prior to APR-246 infusion
	At end of infusion	+/-5 min relative to the end of infusion
	After infusion	30-60 min AFTER infusion

*From Cycle 2 (C2) in patients selected for ECG Holter testing.

8.5 Pharmacodynamics

8.5.1 Tumor Biopsies

Archived tumor tissue (formalin fixed paraffin embedded [FFPE] sections) from all patients will be reviewed by a gynecological pathologist to confirm the diagnosis of HGSOE, and positive IHC staining for p53. In addition, these samples will be used to determine p53 status by IHC by a central laboratory.

Additional analysis may include biomarkers and evaluation of tumor cell DNA.

Where possible paired tumor biopsies should be collected: one prior to treatment and the other during treatment (optimally within the last 30 minutes of the APR-246 infusion on day 3 of the first cycle, however a biopsy obtained at the end of the APR-246 infusion on day 2 is acceptable).

Two tumor cores will be taken at each biopsy, one will be flash frozen and one will be formalin fixed.

The choice of the tumor lesion is at the Investigator's discretion. The reasons for failure to obtain a biopsy must be recorded in the eCRF. If the pretreatment tumor biopsy is not obtained, no further tumor biopsies will be attempted.

Any lesion that is used for biopsy purposes should be recorded a non-target lesion only.

The following assessments may be performed by Aprea Therapeutics AB or a central laboratory appointed by Aprea Therapeutics AB (please refer to Laboratory Manual).

- Immunohistochemistry for tumor cellularity and p53 protein staining and other IHC markers (i.e., *BRCA1*, endoplasmic reticulum stress markers)
- RNA/DNA extraction for microarray tumor gene expression profiling
- Proteomics – lysates for reverse phase proteomics.

Specimens may be stored for future evaluation of APR-246 in target tissue.

The quality and quantity of the biopsy will determine which analyses are to be performed. The mutational analyses will be done in batches and the results will not be reported to the trial site during the treatment period.

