5.0 SELECTION AND WITHDRAWAL OF PATIENTS

5.1 Inclusion Criteria

To be eligible to participate in this study, patients must meet all of the following inclusion criteria:

1. Archived sections from the original formalin fixed paraffin embedded sample reviewed by a gynecological pathologist confirming HGSOE, high grade serous peritoneal cancer or primary fallopian tube cancer and positive immunohistochemistry staining for p53 assessed according to the local methodology (as detailed in the laboratory manual). Cases that do not show p53 staining will not be included.
2. Disease progression between 4 weeks and 6 months after the last platinum-based treatment was administered.
3. At least a single (RECIST 1.1) measurable lesion.
4. Adequate organ function prior to registration:
 - a) Bone marrow reserve
 - Absolute neutrophil count (ANC) $\geq 1.5 \times 10^9/L$
 - Platelets $\geq 100 \times 10^9/L$
 - Hemoglobin ≥ 9 g/dL
 - b) Hepatic
 - Total bilirubin level $< 1.5 \times$ upper limit of normal (ULN) without hepatic metastasis, and $< 4 \times$ ULN with hepatic metastasis
 - Alanine aminotransferase (ALT) and aspartate aminotransferase (AST) $< 2.5 \times$ ULN without hepatic metastasis, and $< 4 \times$ ULN with hepatic metastasis
 - c) Renal
 - Calculated creatinine clearance > 30 mL/min calculated per local practice
 - d) Electrolytes
 - Potassium within institutional normal ranges.
5. Toxicities from previous cancer therapies (excluding alopecia) must have recovered to grade 1 (defined by National Cancer Institute [NCI] Common Terminology Criteria for Adverse Events [CTCAE] version 4.0). Chronic stable grade 2 peripheral neuropathy secondary to neurotoxicity from prior therapies may be considered on a case by case basis by the Principal Investigator.
6. If of childbearing potential, negative pretreatment serum pregnancy test.
7. If of childbearing potential, willing to use an effective form of contraception (see below)

during chemotherapy treatment and for at least 6 months thereafter. Such methods include the following (if using hormonal contraception, this method must be supplemented with a barrier method, preferably male condom):

- combined (estrogen and progestogen containing) hormonal contraception associated with inhibition of ovulation:
 - oral
 - intravaginal
 - transdermal
 - progestogen-only hormonal contraception associated with inhibition of ovulation:
 - oral
 - injectable
 - implantable
 - intrauterine device (IUD)

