3. Optional rhythm strip performed using limb leads of 12-lead ECG machine, after the end of APR-246 infusion.
4. These assessments will be discontinued once sufficient evaluable data has been collected.
5. An optional tumor biopsy to be performed prior to Day 1 APR-246 infusion and on Cycle 1 Day 3, as per laboratory manual.
6. CT scan/MRI at the end of Cycle 2 (within 4 days prior to the start of Cycle 3), and at the end of Cycle 4 (within 4 days prior to the start of Cycle 5) and every two cycles thereafter. In patients who have discontinued therapy without progression, scans will be performed every 8 weeks until progression has occurred.
7. Blood sample taken within 72 hours of pretreatment biopsy.
8. Blood samples taken before infusion of APR-246 in Cycles 1, 2 and 6.
9. Blood samples should be taken at each follow-up visit before progression and at progression, as per laboratory manual.
10. Pharmacokinetics: please refer to Section 8.4.
11. New anticancer treatment to be collected in eCRF during follow up.
12. Follow-up visits should be performed at least every 8 weeks.
13. AEs will be collected throughout the study, from informed consent until 30 days after the last administration of study treatment.

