8.1.1 Measurable Disease

Measurable disease is defined by the presence of at least one measurable lesion. Measurable lesions are defined as those that can be accurately measured in at least one dimension (longest diameter [LD] in the plane of measurement to be recorded) with a minimum size of:

- 10 mm by CT scan (CT scan slice thickness no greater than 5 mm)
- 10 mm caliper measurement by clinical exam (lesions which cannot be accurately measured with calipers should be recorded as non-measurable)
- 20 mm by chest X-ray.

Malignant lymph nodes: To be considered pathologically enlarged and measurable, a lymph node must be ≥ 15 mm in short axis when assessed by CT scan (CT scan slice thickness no greater than 5 mm).

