8.3.2.2 Evaluation of Best Overall Response by RECIST

The best overall response is the best response recorded from the start of the treatment until disease progression/recurrence (taking as reference for progressive disease the smallest measurements

recorded since the treatment started). The patient’s best overall response assignment will depend on findings of both target and non-target disease and will also take into consideration the appearance of new lesions.

It is assumed that at each protocol-specified time point, a response assessment occurs. Table 5 provides a summary of the overall response status calculation at each time point for patients who have measurable disease at pretreatment. When patients have non-measurable disease, Table 6 should be used.

Table 5. Time Point Response: Patients With Target (+/- Non-target) Disease

Target Lesions	Non-target Lesions	New Lesions	Overall Response
CR	CR	No	CR
CR	Non-CR / non-PD	No	PR
CR	Not evaluated	No	PR
PR	Non-PD or not all evaluated	No	PR
SD	Non-PD or not all evaluated	No	SD
Not all evaluated	Non-PD	No	NE
PD	Any	Yes or No	PD
Any	PD	Yes or No	PD
Any	Any	Yes	PD

CR=complete response, PR=partial response, SD=stable disease, PD=progressive disease, NE=not evaluable

Table 6. Time Point Response: Patients With Non-target Disease Only

Non-target Lesions	New Lesions	Overall Response
CR	No	CR
Non-CR / non-PD	No	Non-CR / non-PD*
Not all evaluated	No	NE
Unequivocal PD	Yes or No	PD
Any	Yes	PD

CR=complete response; PD=progressive disease; NE=not evaluable
* Non-CR/non-PD is preferred over SD for non-target disease

Best response determination for studies where confirmation of CR or PR is required: Complete or partial responses may be claimed only if the criteria for each are confirmed by a repeat assessment at least 4 weeks later. In this circumstance, the best overall response can be interpreted as in Table 7.

Table 7. Best Overall Response When Confirmation of CR and PR is Required

Overall Response First Time Point	Overall Response Subsequent Time Point	Best Overall Response
CR	CR	CR
CR	PR	SD, PD or PR*
CR	SD	SD provided minimum criteria for SD duration met, otherwise PD
CR	PD	SD provided minimum criteria for SD duration met, otherwise PD
CR	NE	SD provided minimum criteria for SD duration met, otherwise NE
PR	CR	PR
PR	PR	PR
PR	SD	SD
PR	PD	SD provided minimum criteria for SD duration met, otherwise PD
PR	NE	SD provided minimum criteria for SD duration met, otherwise NE
NE	NE	NE

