9.3 Analysis Populations

The following populations will apply:

Safety Evaluable Population: All patients who received study medication (APR-246 or PLD) will be considered evaluable for safety regardless of the duration of treatment. This population will be used

to summarize all safety parameters.

Efficacy Evaluable Population: All patients with pretreatment measurable disease by RECIST 1.1 who have at least one radiographic assessment after pretreatment or discontinue study medication early due to disease progression and have a p53 mutation will be considered evaluable for efficacy. The efficacy-evaluable population will be the primary analysis population for efficacy.

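### Biopsy of a patient's only measurable lesion leaves her with no target lesion, so a partial response cannot be scored, yet on the plain reading she still counts in the response-rate denominator

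*Combined protocol and SAP*

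**What the plan says.** **Entry.** Section 5.1, item 3, asks for "At least a single (RECIST 1.1) measurable lesion". One is enough.

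**Target lesions.** Section 8.1.3 makes all measurable lesions target lesions, up to two per organ and five in total.

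**Biopsy.** Table 4, footnote 5 (Section 7.1) provides for "An optional tumor biopsy to be performed prior to Day 1 APR-246 infusion and on Cycle 1 Day 3". Section 8.5.1 encourages it: "Where possible paired tumor biopsies should be collected". The lesion is chosen by the investigator, and a failure to obtain a biopsy must be explained in the eCRF. Section 8.5.1 then adds: "Any lesion that is used for biopsy purposes should be recorded a non-target lesion only". It makes no exception for a sole measurable lesion.

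**Scoring.** Section 8.3.1 defines partial response (PR) only as a fall of at least 30% in the sum of target-lesion diameters. In Section 8.3.2.2, Table 5 is for patients with measurable disease and is laid out by target-lesion status. Table 6 is introduced with "When patients have non-measurable disease, Table 6 should be used", but its title covers patients with non-target disease only. Its outcomes are CR, non-CR/non-PD, NE and PD. It has no PR row.

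**Denominator.** The efficacy-evaluable population in Section 9.3, which is primary for efficacy, starts from "All patients with pretreatment measurable disease by RECIST 1.1". It adds a post-baseline scan (or early stop for progression) and a p53 mutation. It does not ask for a target lesion. Section 8.1.1 ties measurability to lesion size: "Measurable disease is defined by the presence of at least one measurable lesion".

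**The concern.** The rules on target lesions, biopsy, scoring and evaluability were each written for the usual patient with several lesions. In a patient with exactly one measurable lesion they can meet badly. Section 8.1.3 makes that lesion a target. Section 8.5.1, if it is biopsied, makes it non-target. The protocol does not say which prevails.

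If 8.5.1 prevails, tumor shrinkage that would otherwise be a PR cannot be recorded as one. The primary endpoint is the RECIST 1.1 response rate, and both decision thresholds are low: at least 2 responses in 16 to continue, and at least 5 in 25 to reject the null. One lost PR can therefore change a decision for a reason unrelated to the drug. Sites could also score identical patients differently.

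**Working it through.** **Step 1: follow one patient through the text.** Assume one measurable lesion, chosen for biopsy.

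| Question | Section | Result |
|---|---|---|
| Eligible? | 5.1, item 3 | Yes |
| Status of the lesion? | 8.1.3 against 8.5.1 | Target under the first, non-target under the second; no precedence |
| PR possible if non-target? | 8.3.1 | No: there is no target-lesion sum |
| Which table? | 8.3.2.2 | Table 5 needs target lesions; Table 6 fits by its title but is introduced for non-measurable disease |
| CR possible? | 8.3.2, Table 6 | Yes: all non-target lesions gone and tumor marker normal |
| Efficacy-evaluable? | 8.1.1, 9.3 | Yes on the plain reading: the lesion is measurable by size, and no target lesion is required |

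Section 6.6 handles a parallel case: irradiation of an index lesion makes the patient non-evaluable for response rate and PFS. Biopsy has no equivalent rule.

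**Step 2: reproduce the stated design figures.** Section 9.1 gives n1 = 16 (stop at 1 or fewer responses), N = 25 (reject at 5 or more), null 10% and alternative 30%.

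P(reject) = sum over x = 2 to 16 of P(X1 = x) × P(X2 ≥ 5 − x), with X1 ~ Bin(16, p) and X2 ~ Bin(9, p).

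- p = 0.30: 0.0732×0.5372 + 0.1465×0.8040 + 0.2040×0.9596 + P(X1 ≥ 5) = 0.0393 + 0.1178 + 0.1958 + 0.5501 = **0.9030** (stated 90.3%).
- p = 0.10: 0.0145 + 0.0321 + 0.0315 + 0.0170 = **0.0951** (stated 9.5%).

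The same formula with 14 then 11 patients gives the Sub-Study 89.06% power and 9.08% type I error (stated 89% and 9.1%).

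**Step 3: effect of k affected patients.** Assumptions: exactly k of the 25 evaluable patients cannot respond, they fall at random across the two stages, CR is ignored, and the thresholds are unchanged. If j of the k fall in stage 1:

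P(reject) = sum over j of [C(16, j) × C(9, k − j) / C(25, k)] × P(reject with 16 − j and 9 − k + j patients able to respond).

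For k = 1 and p = 0.30: (16/25)×0.8802 + (9/25)×0.8843 = 0.8817.

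| k of 25 (assumed) | Main power at 30% | Main type I error at 10% | Main futility stop at 30% | Sub-Study power at 30% |
|---|---|---|---|---|
| 0 | 90.3% | 9.51% | 2.6% | 89.1% |
| 1 | 88.2% | 8.25% | 3.2% | 86.8% |
| 2 | 85.6% | 7.09% | 3.9% | 84.2% |
| 3 | 82.7% | 6.02% | 4.8% | 81.1% |

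**Step 4: allow for CR.** Let each patient be affected with probability 2/25 = 8%, and let a share c of responses be CR (assumed). The effective rate is 0.30 × [1 − 0.08 × (1 − c)].

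- c = 0: rate 0.2760, Main Study power 85.2%.
- c = 0.10: rate 0.2784, power 85.8%.
- c = 0.20: rate 0.2808, power 86.4%.

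Allowing for CR narrows the loss slightly.

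**The case against.** Several points on the other side have force.

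- **The entry criterion and the biopsy rule do not contradict each other.** A reader might infer that they do. Section 5.1 sets a minimum for entry and Section 8.5.1 says how to record a biopsied lesion; biopsying another lesion, or none, satisfies both. The direct conflict is between 8.1.3 and 8.5.1. One could read those two together as meaning that a sole measurable lesion should be left alone. That is sensible, but nothing in the protocol says it.
- **Her place in the denominator is not fully settled.** By its introductory sentence Table 6 is for non-measurable disease. If she were classed that way, Section 9.3 would exclude her and the response rate would not be biased, although an evaluable patient would be lost. The size-based definition in 8.1.1 favors keeping her in. It is the plain reading, not an explicit rule.
- **Several conditions must coincide.** She must have exactly one measurable lesion, accept an optional biopsy, and have that lesion chosen. The documents give no frequency for any of these.
- **The bias is conservative.** It cannot inflate a false-positive claim.
- **Other documents may help.** The laboratory manual, which is not available here, may guide lesion choice, and Section 9.2 promises further analysis detail in a SAP before data lock. Neither would repair the recording and scoring rules that the protocol itself states.

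These points limit the size and certainty of the problem. They do not close the gap: an investigator who follows Section 8.5.1 as written can make a PR unscorable.

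**Conclusion.** The point holds as a gap between Sections 8.1.3 and 8.5.1 that reaches the primary endpoint through 8.3.1, 8.3.2.2 and 9.3. If a sole measurable lesion is biopsied and recorded as non-target, PR is unavailable whichever table is used. On the plain reading the patient stays evaluable and can respond only through CR.

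A reader might go further and infer that the stated 90.3% power is wrong, or that a loss of 2 to 8 points should be expected. The documents support neither. The stated figures reproduce exactly, and the number of affected patients is unknown and may be zero. The losses of 2.1, 4.7 and 7.6 points (90.3% less 88.2%, 85.6% and 82.7%) are a range for an assumed 1, 2 or 3 patients of 25 with no CR. Nor is each such patient a certain non-responder, since CR remains open.

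This is a cheap improvement to the protocol, not an error in the design calculation.

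**What to change.** In Section 8.5.1, state that the optional study biopsy is taken from a lesion only if at least one other measurable lesion remains as a target lesion. Align Section 8.1.3 by saying that a biopsied lesion is left out of the target set on that condition, and carry the same rule into the laboratory manual. With this in place, no patient loses her only target lesion to the study biopsy, so the questions about Table 5, Table 6 and evaluability do not arise from it.

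The cost is a sentence in each place and slightly fewer optional paired biopsies. Sample size, thresholds and the stated operating characteristics are unchanged.

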8.6 Exploratory Biomarker Research

Plasma, whole blood and tumor samples will be collected from all patients and stored for retrospective exploratory analyses. These analyses may include (but are not necessarily limited to):

- Predictive markers of efficacy, tolerability and clinical pharmacology
- Biomarkers of acquired or innate resistance to APR-246

- Circulating free tumor DNA

The results of the exploratory biomarker research will be reported separately and will not be part of the Clinical Study Report.

Blood samples will be taken pre-treatment for collection of germ line DNA in order to allow comparison of germ-line and tumor cell DNA sequence. Refer to Laboratory Manual for detailed instructions.

The results of exploratory biomarker research may be pooled with data from other studies with APR-246 to generate hypotheses to be tested in future studies.

8.7 Biological Sample Handling

Details of sample collection, processing, shipping and storage will be described in the laboratory manual. Each sample for exploratory research will be identified with the study number and patient enrollment number. In this way exploratory biomarker and genetic data may be correlated with clinical data. Samples will be destroyed in the case of withdrawal of consent and regulatory audit enabled. Where genetic analysis will be undertaken the processes adopted for the coding and storage of samples will be more stringent in order to maintain patient confidentiality. As an added precaution, irrespective of the type of sample, the DNA sample will be assigned a unique number replacing the information on the sample tube. Thereafter, the DNA sample will be identifiable by the unique DNA number only. The DNA number will be used to identify the sample and corresponding data at the Aprea Therapeutics AB's designated contract laboratory. No personal details identifying the individual will be available to any person (Aprea Therapeutics AB or contract laboratory staff) working with the DNA. The samples and data for genetic analysis in this study will be single coded. The link between the patient enrollment code and the DNA number will be maintained and stored in a secure environment, with restricted access. The link will be used to identify the relevant DNA samples for analysis, facilitate correlation of genotypic results with clinical data, allow regulatory audit and to trace samples for destruction in the case of withdrawal of consent when the patient has requested disposal/destruction of collected samples not yet analyzed.

8.8 Chain of Custody of Biological Samples

A full chain of custody is maintained for all samples throughout their lifecycle. The Principal Investigator at each center keeps full traceability of collected biological samples from the patients while in storage at the center until shipment or disposal (where appropriate) and keeps documentation of receipt of arrival. The Principal Investigator will also ensure that access to the samples while in storage at the study center will be limited only to those people for whom access is required. The sample receiver keeps full traceability of the samples while in storage and during use until used or disposed of or until further shipment and keeps documentation of receipt of arrival.

Aprea Therapeutics AB keeps oversight of the entire life cycle through internal procedures, monitoring of study sites and auditing of external laboratory providers. Samples retained for further use will be registered in the Aprea Therapeutics AB biobank system during the entire life cycle. Samples will be stored for up to 15 years.

